APPENDIX 9: CLINICAL EVALUATION OF HEPATIC INJURY

Hepatic injury is defined by the following alterations of liver parameters:

- For patients with normal liver function at baseline: an elevation of AST and/or ALT $\geq 3 \times$ ULN combined with an elevation of bilirubin $\geq 2 \times$ ULN measured in the same blood draw sample
- For patients with impaired liver function at baseline: an elevation of AST and/or ALT $> 5 \times$ ULN combined with an elevation of total bilirubin > 2 times ULN measured in the same blood draw sample
- For all patients, marked peak aminotransferase (ALT and/or AST) elevations $\geq 10 \times$ ULN with or without concurrent elevation of bilirubin.

These laboratory findings constitute a hepatic injury alert, and patients showing these laboratory abnormalities need to be followed up according to the procedures below. In case of clinical symptoms of hepatic injury (icterus, unexplained encephalopathy, unexplained coagulopathy, right upper quadrant abdominal pain, etc.) without laboratory results (ALT, AST, and total bilirubin) available, the Investigator should make sure these parameters are analyzed, if necessary in an unscheduled blood test. If the results meet the criteria of a hepatic injury alert, the procedures described below and the drug-induced liver injury (DILI) checklist should be followed.

Repeat the following laboratory tests according to the following criteria:

Patients with liver function test (LFT) value(s) within normal limits at baseline:

Alanine aminotransferase (ALT), aspartate aminotransferase (AST), and bilirubin (total and direct) within 48 to 72 hours. If ALT and/or AST ≥ 3 times upper limit of normal (ULN) combined with an elevation of total bilirubin ≥ 2 times ULN are confirmed, results of the laboratory parameters described below must be made available to the Investigator and to Archigen as soon as possible.

Patients with elevated LFT value(s) at baseline:

Repeat the following laboratory tests: ALT, AST, and bilirubin (total and direct) within 48 to 72 hours. If ALT and/or AST ≥ 5 times ULN combined with an elevation of total bilirubin ≥ 2 times ULN are confirmed, results of the laboratory parameters described below must be made available to the Investigator and to Archigen as soon as possible.

Patients with elevated total bilirubin at baseline due to hepatic infiltration by follicular lymphoma (FL), Gilbert's Syndrome, or hemolysis:

The threshold to qualify for repeat laboratory tests is defined as elevation of hepatic enzymes based on the above criteria, combined with concurrent elevation of total bilirubin above baseline.

In addition:

- obtain a detailed history of current symptoms, concurrent diagnoses, and medical history according to the DILI checklist (see Tables 1 and 2 below);
- obtain history of concomitant drug use (including non-prescription medications, herbal and dietary supplement preparations), alcohol use, recreational drug use, and special diets according to the DILI checklist (see Tables 1 and 2 below);
- obtain a history of exposure to environmental chemical agents (consider home and work place exposure) according to the DILI checklist (see Tables 1 and 2 below);

and report these via the eCRF.

Clinical chemistry

- Alkaline phosphatase, albumin, prothrombin time or International Normalized Ratio, creatine kinase, creatine kinase muscle-brain, coeruloplasmin, α -1 antitrypsin, transferrin, amylase, lipase, fasting glucose, cholesterol, triglycerides, cholinesterase

Serology

- Hepatitis A (anti-IgM, total Ig), hepatitis B (hepatitis B surface antigen [HBsAg], Anti-HBs, DNA), hepatitis C (anti-hepatitis C virus [HCV], RNA if anti-HCV positive), hepatitis D (anti-IgM, total Ig), hepatitis E (anti-hepatitis E virus [HEV], anti-HEV IgM, RNA if anti-HEV IgM positive), anti-Smooth Muscle antibody (titer), anti-nuclear antibody (titer), anti-liver-kidney microsomes antibody, anti-mitochondrial antibody, Epstein Barr Virus (virus capsid antigen [VCA] IgG, VCA IgM), cytomegalovirus (IgG, IgM), herpes simplex virus (IgG, IgM), varicella (IgG, IgM), parvovirus (IgG, IgM), toxoplasmosis (IgG, IgM)

Hormones, tumor marker

- Thyroid stimulating hormone

Hematology

- Complete blood count (including differential counts)

Provide abdominal ultrasound to rule out biliary tract, pancreatic or intrahepatic pathology, eg, bile duct stones or neoplasm.

Initiate close observation of patients by repeat testing of ALT, AST, and total bilirubin (with fractionation by total and direct) at least weekly until the laboratory ALT and or AST

abnormalities stabilize or return to normal, then according to the CTP. Depending on further laboratory changes, additional parameters identified, eg, by reflex testing, will be followed up based on medical judgment and GCP.

Assessment of drug-induced liver injury (DILI):

Source: Lee WM and Senior JR. Recognizing drug-induced liver injury: current problems, possible solutions. Toxicol Pathol. 2005;33(1):155-64.

The type of liver injury is determined first: hepatocellular, cholestatic or mixed (see Table 1).

Table 1: Determining the Type of Acute Liver Injury

Ratio (R) of serum activities of ALT/ALP, in xULN, measured together at time liver injury first recognized	
Hepatocellular	$R \geq 5$, OR (ALT $> 2 \times$ ULN and ALP in normal range)
Cholestatic	$R \leq 2$, OR (ALP $> 2 \times$ ULN and ALT in normal range)
Mixed	$2 < R < 5$ AND (ALT $> 2 \times$ ULN and ALP $>$ULN)

Checklist criteria are then scored according to Table 2.

Table 2: Abbreviated DILI checklist

Criteria	Explanation	Score
Time to onset of liver injury, from initial exposure to drug	Suggestive 2; compatible, 1; inconclusive, 0. (if no information, case insufficiently documented; if incompatible, unrelated)	0 to 2
Course of the reaction	Highly suggestive, 3; suggestive 2; compatible, 1; inconclusive or no data, 0; against a role for the drug, -2	-2 to 3
Known risk factors for DILI; Alcohol use; Age \geq 55	None, 0; one validated risk factor, 1; two or more validated risk factors, 2	0 to 2
Concomitant drug exposure	None, no information, or incompatible time to onset, 0; time compatible but not known hepatotoxin, -1; time compatible and known hepatotoxin, -2; definitely caused by other agent, -3	0 to -3
Alternative nondrug cause	Ruled out (not hepatitis A, B, or C; not alcohol-induced [AST/ALT = 2]; no gall stones or biliary tract disease by ultrasound; no recent hypotension), 2; not fully investigated, some ruled out, 1 to -2, depending on how many; probable, -3	-3 to 2
Previous information on drug	Not known hepatotoxin, 0; published as hepatotoxic, 1; labeled as hepatotoxin, 2	0 to 2
Response to rechallenge	Positive, 3; compatible, 1; not done, not interpretable, 0; negative, -2	-2 to 3

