5.2.5 Clinical Laboratory Evaluations

A list of clinical laboratory assessments to be measured is provided in Table 2. Additional parameters may be measured in the event of AEs, and as necessary for patient care.

If any laboratory findings meet the definition of hepatic injury (see Appendix 9), patients should be managed according to the instructions in Appendix 9.

Blood and urine samples will be collected at the times indicated in Table 1.

Table 2 Clinical Laboratory Assessments

Hematology	Hemoglobin, hematocrit, platelets, white blood cells with differentiation, and neutrophils (absolute counts)
Clinical chemistry (serum)	Creatinine, alkaline phosphatase, total bilirubin, AST, ALT, total protein, albumin, calcium, BUN, phosphorus, uric acid, and electrolytes (sodium, potassium, chloride)
Urinalysis	Glucose, protein, blood, and leukocytes
Virology	Hepatitis C virus antibodies, human immunodeficiency virus, hepatitis B surface antigen, hepatitis B core antibody (total and immunoglobulin M), and HBV DNA
Pregnancy testing	hCG (serum or urine, as appropriate)
Tumor markers (serum)	β 2 microglobulin and LDH

Note: Additional parameters may be measured in the event of AEs, and as necessary for patient care.
 ALT alanine aminotransferase; AST aspartate aminotransferase; BUN blood urea nitrogen;
 HBV DNA hepatitis B virus deoxyribonucleic acid; hCG human chorionic gonadotropin;
 LDH lactate dehydrogenase

It is the responsibility of the Investigator or Sub-investigator to review the results of all laboratory tests as they become available. For each abnormal laboratory test result, the Investigator or Sub-investigator needs to ascertain if this is an abnormal (i.e., clinically significant) change from baseline for that individual patient. This determination, however, does not necessarily need to be made the first time an abnormal value is observed. The Investigator or Sub-investigator may repeat the laboratory test or conduct additional tests to verify the results of the original clinical laboratory tests. If this laboratory value is determined by the Investigator or Sub-investigator to be a clinically significant change from baseline for that patient, it is considered to be an AE (Section 6.7).

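### Appendix 9 makes isolated ALT/AST ≥10 x ULN a hepatic injury alert but gives it no confirmation branch: both sentences that mandate the extended laboratory results also require raised bilirubin

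*Protocol*

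**What the plan says.** Protocol Section 5.2.5 refers any laboratory finding that meets the hepatic injury definition to Appendix 9: "patients should be managed according to the instructions in Appendix 9".

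Appendix 9 then gives three alert criteria:

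1. Normal liver function at baseline: AST and/or ALT ≥3 x ULN with bilirubin ≥2 x ULN in the same sample.
2. Impaired liver function at baseline: AST and/or ALT >5 x ULN with total bilirubin >2 x ULN in the same sample.
3. "For all patients, marked peak aminotransferase (ALT and/or AST) elevations" of at least 10 x "ULN with or without concurrent elevation of bilirubin".

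All three are alerts, and "patients showing these laboratory abnormalities need to be followed up according to the procedures below".

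The procedures are split by baseline status. With normal LFTs, ALT, AST and bilirubin are repeated within 48 to 72 hours. If ALT and/or AST ≥3 x ULN is found again, "combined with an elevation of total bilirubin ≥ 2 times ULN are confirmed, results of the laboratory parameters described below must be made available" as soon as possible. With elevated LFTs the repeat is the same and the condition reads: "If ALT and/or AST ≥ 5 times ULN combined with an elevation of total bilirubin ≥ 2 times ULN are confirmed". For bilirubin raised at baseline (infiltration by FL, Gilbert's Syndrome or hemolysis), the threshold for the repeat tests themselves is an enzyme rise "combined with concurrent elevation of total bilirubin above baseline".

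The appendix then lists the histories for the DILI checklist, the laboratory panel (which includes HBsAg, anti-HBs and hepatitis B DNA), an abdominal ultrasound, and at-least-weekly ALT, AST and bilirubin.

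**The concern.** Criterion 3 says that bilirubin is irrelevant to the alert. The steps that act on an alert then bring bilirubin back as a condition. A site with a patient at ALT 12 x ULN and normal bilirubin has two defensible readings. On one, the general instruction applies and the whole work-up follows. On the other, the confirmation condition is not met and the extended results are not required.

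Hepatitis reactivation is an adverse event of special interest (Section 6.4), and Section 4.11.3 attaches immediate consequences to it. The panel affected by the ambiguity holds the hepatitis B tests. After screening, scheduled HBV testing is confined to patients with occult or prior infection. Even for them, Table 1 and Appendix 10 schedule none at Weeks 2, 3 and 4, although clinical chemistry is drawn at those dosing visits. With about 165 sites, uneven work-up of the same laboratory picture is a realistic result. What is at stake is patient safety and consistent ascertainment of a safety event; no effect on the ORR analysis is shown.

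**Working it through.** There is no sample size, power or event figure to reproduce. The check sets the definition beside the triggers and applies both to example patients. The values are illustrative, in multiples of ULN.

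**Definition against trigger**

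| Baseline status | Alert definition | Condition for repeat tests | Condition for mandatory extended results |
|---|---|---|---|
| Normal | ALT/AST ≥3 and bilirubin ≥2, or ALT/AST ≥10 alone | none beyond the alert | ALT/AST ≥3 and bilirubin ≥2 |
| Elevated/impaired | ALT/AST >5 and bilirubin >2, or ALT/AST ≥10 alone | none beyond the alert | ALT/AST ≥5 and bilirubin ≥2 |
| Raised bilirubin | no separate definition; ALT/AST ≥10 alone applies to all | enzyme rise and bilirubin above baseline | no separate sentence |

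The right-hand column has no entry that an isolated ≥10 x ULN value can meet. The panel itself is a list of test names under headings. The instructions that reach it are the two conditional sentences and the general sentence sending all alerts to the procedures.

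**Cases for criterion 3**

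- **A.** Normal baseline, ALT 12, bilirubin 1, unchanged on repeat. Alert: 12 ≥ 10, yes. Confirmation: 12 ≥ 3, yes; 1 ≥ 2, no. Not met.
- **B.** Elevated LFTs at baseline, same values. Alert: yes. Confirmation: 12 ≥ 5, yes; 1 ≥ 2, no. Not met.
- **C.** Raised bilirubin at baseline, ALT 12, bilirubin at its baseline level. Alert: yes. Repeat tests: bilirubin above baseline, no. Not met.
- **D.** Normal baseline, ALT 12, bilirubin 1 at first draw and 2.2 on repeat. Alert: yes. Confirmation: 12 ≥ 3 and 2.2 ≥ 2, yes. Met.

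The gap is present in all three baseline groups while bilirubin stays unraised, and closes in D.

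**Cases for the raised-bilirubin group**

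- **E.** Gilbert's Syndrome (exempt from the bilirubin limit in inclusion criterion 8), baseline bilirubin 2.5, now ALT 6 and bilirubin 2.4. If classed as normal liver function: 6 ≥ 3 and 2.4 ≥ 2, alert. If classed as impaired: 6 > 5 and 2.4 > 2, alert. Under that group's rule for repeat tests: 2.4 > 2.5, no. An alert on either classification, yet below the repeat-test threshold.
- **F.** Hemolysis, baseline bilirubin 1.2, now ALT 6 and bilirubin 1.5. Repeat tests: 1.5 > 1.2, qualifies. Alert: 1.5 is below 2 and 6 is below 10, no. Repeat tests without an alert, so no follow-up is lost.

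**Inequality signs.** With impaired baseline function, ALT exactly 5 and bilirubin exactly 2 fail the definition (>5 and >2) but pass the confirmation step (≥5 and ≥2).

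**The case against.** A reader might infer that an isolated ≥10 x ULN alert can never lead to the extended work-up. The documents do not support that. The general sentence covers all three criteria, so a site may apply the full procedures. For alerts found after clinical symptoms, Appendix 9 repeats that the procedures and the DILI checklist should be followed, with no bilirubin condition. The conditional sentences can also be read as governing how fast results reach the investigator and sponsor, rather than whether the tests are done. Case D shows the condition can be met on repeat. The text is contradictory; it does not clearly exclude the work-up.

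A reader might also infer that nothing in the procedures applies to criterion 3. That is wrong too. Patients with normal or elevated LFTs get the repeat tests whatever the bilirubin, and the histories, ultrasound and weekly monitoring have no bilirubin condition of their own. The DILI checklist scores whether hepatitis A, B or C was ruled out, which points toward hepatitis testing, although it also allows a score for incomplete investigation.

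A third inference is that HBV reactivation would be missed. HBsAg-positive patients are excluded, patients with occult or prior infection are re-tested at each visit from Week 5, and investigators may add tests at their discretion (Section 5.2.5, Table 1). The panel is a mandated route, not the only one.

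Finally, a separate rule for raised baseline bilirubin may be deliberate, case F costs no follow-up, and the difference in signs matters only at exact boundary values.

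These points stand and narrow the issue. They do not remove it: discretion and a generous reading are not a stated pathway, and case E is inconsistent however Gilbert's Syndrome is classed.

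**Conclusion.** Appendix 9 contradicts itself on the isolated ≥10 x ULN alert. The alert applies to all patients regardless of bilirubin and must be followed up, but no confirmation branch exists for it, and both sentences mandating the extended results require total bilirubin ≥2 x ULN. In the raised-baseline-bilirubin group even the repeat tests depend on bilirubin above baseline, so a patient can be an alert and still fall short of them. The difference in inequality signs is a minor, editorial matter.

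The size can be shown only by case, because neither document gives rates of liver enzyme elevation. The conclusion assumes that bilirubin stays below the relevant condition on repeat and that a site reads the confirmation sentences literally. It does not extend to a claim that reactivation would go undetected, or to any effect on efficacy. It is worth correcting because it concerns a safety rule and can be resolved within one appendix.

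**What to change.** Reconcile the alert definitions in Appendix 9 with the repeat-test and confirmation triggers. Each of the three criteria, and the group with raised bilirubin at baseline, should lead to one stated pathway that says what is repeated, what confirms the alert, and which results must then be supplied. Use the same thresholds and inequality signs in the definition and in the triggers. If the separate rule for raised baseline bilirubin is intended, say how it relates to the general definition. The sponsor's medical team decides which thresholds apply; this review takes no view on that.

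The cost is an amendment to one appendix, since Section 10.7 requires permanent changes to be handled that way, with communication to sites. All the tests are already listed, but depending on the pathway chosen, a few patients may have more of them.

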APPENDIX 10: SCHEDULE OF ASSESSMENTS

1. Screening (Visit 1 – Study Days -30 to 0)

The following screening procedures will be performed within 30 days prior to the first day of blinded study drug administration unless otherwise stated.

- Informed consent (must be obtained prior to the patient undergoing any study specific procedures and may occur prior to the 30 day screening period).
- Review inclusion /exclusion criteria.
- Record screening visit in the IXRS.
- Confirm diagnosis of Grade 1-3a, CD20+ FL and ensure tissue or slide is available for the retrospective central pathology review (Appendix 2). If a biopsy has not been performed within the previous 24 months prior to screening visit, a new biopsy is required to confirm that the histology is unchanged.
- Evaluate FL signs and symptoms and ensure the patient is not experiencing B symptoms.
- Ensure the patient is Ann Arbor Stage II, III, or IVA (Appendix 5).
- Collect information for FLPI-2 (Appendix 3).
- Collection of demographic information.
- Medical and surgical history.
- Adverse events.
- Prior and current medications.
- Physical examination (PE) The PE should include assessment of general appearance, skin, head, neck, throat, lymph nodes, thyroid, abdomen, cardiovascular, neurological, musculoskeletal/extremities, and respiratory systems, as appropriate, and consistent with local standard of care. Body weight will be measured. Height will be measured at screening only. The PE must include lymph nodes, liver and spleen. Any specific signs or symptoms that are medically significant should be reported. Particular attention should be paid to any new or worsening neurological symptoms or signs that may be suggestive of PML (typical symptoms are diverse and include cognitive or visual disorders, hemiparesis, confusion and behavioral disorders).
- Vital signs, including systolic and diastolic blood pressure, pulse, respiratory rate, and body temperature. To be measured after the patient has been in a sitting/lying down position for at least 5 minutes.

- ECOG performance status assessment
- 12-lead electrocardiogram (ECG).
- Laboratory testing including hematology, blood chemistry, urinalysis, serum β 2 microglobulin, lactate dehydrogenase (LDH), and viral disease screening (hepatitis B surface antigen, hepatitis B core antibody, and hepatitis C antibody, and HIV testing)
- HBV testing - patients with occult or prior hepatitis B infection (defined as positive total HBcAb and negative HBsAg) only.
- TB screen (if required by local regulation or at the investigator's discretion) to be performed according to local practice and local regulatory guidance, unless obtained within 3 months prior to Day 1. A chest X-ray will be required for all patients with a positive TB test to confirm there is no active TB.
- Serum pregnancy test (human chorionic gonadotrophin; hCG) for women of childbearing potential. For definition of childbearing potential, refer to inclusion criterion 9 & 10.
- Contrast enhanced CT scan of neck, chest, abdomen and pelvis and any other areas known or suspected to be involved. A CT scan acquired up to 60 days prior to Day 1 may be used for screening provided that the scan is of sufficient quality according to central review. For Investigators who routinely use PET scans for assessment of their patients, a PET scan may be performed **in addition to** (not instead of) the CT scan at the Investigator's discretion. Combined PET-CT scans may be used only if performed with contrast, and if the resolution is sufficient to allow accurate and consistent comparison of lesion measurements with subsequent CT scans. Where the contrast product is contraindicated, an abdomen-pelvic magnetic resonance imaging scan (MRI) should be performed with a non-contrast chest CT scan.
- Bone marrow biopsy (biopsy specimen up to 60 days prior to Day 1 may be used for screening. To be performed locally and confirmed centrally. Patients with bone marrow biopsies demonstrating lymphoma within the previous year are not required to undergo a repeat bone marrow evaluation prior to study entry. Patients with a prior bone marrow biopsy performed more than 1 year before screening or negative for lymphoma, or with no bone marrow biopsy, will be required to undergo another bone marrow biopsy within 60 days of randomization.

2. Study Period

2.1. Day 1 (Visit 2)

- Review inclusion/exclusion criteria to ensure patient eligibility
- Randomization via IXRS (can be conducted up to 4 days prior to Day 1).
- Note: Randomization will be stratified based on low, intermediate, and high risk patients using the Follicular Lymphoma International Prognostic Index 2 (FLIPI-2).

It is critical that the FLIPI-2 is scored correctly and that this information is entered into the IXRS accurately.

- IXRS study drug assignment.
- PE including body weight.
- Vital signs.
- Prior and concomitant medications.
- Adverse events.
- Laboratory testing including hematology, blood chemistry, urinalysis, serum β 2 microglobulin, and LDH.
- HBV DNA testing in patients with occult or prior hepatitis B infection (defined as positive total HBcAb and negative HBsAg) at screening.
- Urine pregnancy test for female patients of childbearing potential.
- PK / PD (CD19+ B-cell count) sampling at 0 hours (pre-dose), and at the end of infusion (\pm 10 minutes).
- IgG and IgM sampling.
- Immunogenicity sampling prior to dosing.
- Administration of pre-medications.
- Study drug administration.

2.2. Treatment Visits (Visits 3, 4, and 5 – Study Days 8, 15 and 22)

- PE including body weight.
- Vital signs.
- Concomitant medications.
- Adverse events.
- Laboratory testing including hematology, blood chemistry, and urinalysis.
- PK / PD (CD19+ B-cell count) sampling at 0 hours (pre-dose), and at the end of infusion (\pm 10 minutes)
- IgG and IgM sampling
- Immunogenicity sampling prior to dosing (Day 15 only).
- Contact IXRS.

- Administration of pre-medications.
- Study drug administration.

2.3. Follow-up Visits (Visit 6, 7, 8, 9 and 10 –Weeks 5, 12, 20, 28 and 36)

- Physical examination (PE).
- Vital signs.
- ECOG performance status assessment (Weeks 5 and 28 only).
- 12-lead ECG (Week 28 only).
- Concomitant medications.
- Adverse events.
- Laboratory testing including hematology, blood chemistry, urinalysis, serum β 2 microglobulin, and LDH.
- HBV DNA testing in patients with occult or prior hepatitis B infection (defined as positive total HBcAb and negative HBsAg) at screening.
- Ann Arbor staging (Week 28 only).
- Contrast enhanced CT scan of neck, chest, abdomen and pelvis, and any other areas known or suspected to be involved. Assessment permitted up to 4 weeks prior to, or 2 weeks after the Week 28 visit. Optional PET or PET-CT scan in addition to CT scan. MRI where the contrast product is contraindicated. (Weeks 12 and 28)
- Bone marrow biopsy – second biopsy required only for patients with positive findings at screening, to confirm Complete Response (CR) based on investigator's review of CT scan (from Week 12 onwards).
- Serum pregnancy test for female patients of childbearing potential (Week 28 only).
- PK (not in week 36) / PD (CD19+ B-cell count) sampling.
- IgG and IgM sampling
- Immunogenicity sampling.

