Immunogenicity sampling is to be done at Weeks 1, 2, 3, 4, 5, 12, 20, 28, 36, and 52 (EOS). Additionally immunogenicity assessment is also planned when patients show signs or symptoms of immune-response-related adverse events including anaphylaxis (Section 6.4.3) and mucocutaneous reaction (Section 6.4.5)

Safety:

Adverse events (AEs), AESI, physical examination, vital signs, ECG, and standard laboratory tests (including hematology, clinical chemistry, urinalysis, serum β₂ microglobulin, and virology), the proportion of patients achieving B-cell recovery (i.e. ≥ lower limit of normal (LLN) or at least 50% of the baseline value) at Week 12, 20, 28, 36 and 52.

Statistical methods:

Efficacy analyses:

The main endpoint will be ORR, the proportion of patients with an overall response of CR or PR (ORR, CR+PR, defined by IWG, 2007) assessed at Week 28.

Two-sided 95% CIs for the differences between SAIT101 and rituximab (MabThera[®]) in the percentage of patients achieving an overall response (CR+PR) at Week 28 will be computed using the Cochran-Mantel-Haenszel (CMH) method. The adjusted proportion difference in ORR and its 95% Newcombe-Wilson CI will be calculated using CMH weight. The efficacy analyses will be applied for both the per-protocol set (PP set) and the full analysis set (FAS). Primary efficacy analysis will be performed based on FAS. Appropriate sensitivity analyses will be applied to explore the robustness of results.

Categorical variables will be summarized by the number and percentage of patients in each category. Continuous variables will be summarized using number, mean, standard deviation, median, minimum, and maximum values.

Safety analyses:

All reported terms for AEs will be coded using the Medical Dictionary for Regulatory Activities (MedDRA). No statistical testing will be performed for AEs. Treatment-emergent AEs (TEAEs) and SAEs will be summarized by the number and percentage of patients experiencing events by System Organ Class (SOC), Preferred Term (PT), and treatment group; TEAEs by severity and causality will be summarized similarly.

Changes in vital signs and clinical laboratory measurements will be summarized descriptively by visit. Other safety variables will be summarized and listed.

Immunogenicity analyses:

Incidence of HACA and neutralizing antibody at the planned sampling time will be summarized overall and by treatment group.

Pharmacokinetic analyses:

The PK analysis will be performed on the PK/PD sub-population.

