The study has been designed in accordance with the EMA ‘Guideline on similar biological medicinal products containing monoclonal antibodies – non-clinical and clinical issues’ (EMA/CHMP/BMWP/403543/2010)²⁰ and the FDA guidance ‘Scientific Considerations in Demonstrating Biosimilarity to a Reference Product’.²¹

Table 1 Schedule of Assessments

Study Period	Screening ^a	Treatment					Follow-up					Early treatment discontinuation visit ^c	Unscheduled visit ^d
Visit	1	2 (Baseline)	3	4	5	6	7	8	9	10	11		
Week		1	2	3	4	5	12	20	28	36	52/EOS ^b		
Day (± window in days)	-30 days ^a	1	8 ± 1	15 ± 1	22 ± 1	29 ± 3	78 ± 3	134 ± 7	190 ± 7	246 ± 7	365 ± 7		
Assessment													
Informed consent	X												
Inclusion/exclusion criteria	X	X ^e											
Demographics	X												
Medical/surgical history	X												
Study drug													
Contact IXRS	X	X	X	X	X						X	X	
Randomization		X											
Pre-medication		X	X	X	X								
Body weight ^f	X	X	X	X	X	X	X	X	X	X	X	X	X
Study drug infusion ^g		X	X	X	X								
Disease assessments													
Histological confirmation of diagnosis ^h	X												
Ann Arbor staging	X								X			(X ⁱ)	
FLIPI-2 score	X												
Bone marrow biopsy ^j	X								X ⁱ			(X ⁱ)	
Tumor assessment (CT scan ^k)	X						X		X			(X ^k)	X

Study Period	Screening ^a	Treatment				Follow-up						Early treatment discontinuation visit ^c	Unscheduled visit ^d
Visit	1	2 (Baseline)	3	4	5	6	7	8	9	10	11		
Week		1	2	3	4	5	12	20	28	36	52/EOS ^b		
Day (± window in days)	-30 days ^a	1	8 ± 1	15 ± 1	22 ± 1	29 ± 3	78 ± 3	134 ± 7	190 ± 7	246 ± 7	365 ± 7		
Laboratory/safety assessments													
Physical examination ^l	X	X	X	X	X	X	X	X	X	X	X	X	X
Vital signs ^m	X	X ⁿ	X ⁿ	X ⁿ	X ⁿ	X	X	X	X	X	X	X	X
12-lead ECG ^o	X								X		X	X	X
ECOG performance status	X					X			X		X	X	X
Prior/concomitant medication	X	X	X	X	X	X	X	X	X	X	X	X	X
Adverse events	X	X	X	X	X	X	X	X	X	X	X	X	X
Pregnancy test ^p	X	X							X		X	X	X
Clinical chemistry, hematology, and urinalysis ^q	X	X	X	X	X	X	X	X	X	X	X	X	X
Virology screen ^r	X												
HBV testing ^s	X	(X)				(X)	(X)	(X)	(X)	(X)	(X)	(X)	(X)
TB screen ^t	X												X
β2 microglobulin, LDH	X	X				X	X	X	X	X	X	X	X
PK sampling ^u		X	X	X	X	X	X	X	X			X	X
PD sampling ^v		X	X	X	X	X	X	X	X	X	X	X	X
IgG / IgM sampling		X	X	X	X	X	X	X	X	X	X	X	X
Immunogenicity sampling ^w		X	X	X	X	X	X	X	X	X	X	X	X

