- w To be performed by the central laboratory. On infusion visits, the sample should be collected pre-dose. Immunogenicity assessment is also planned when patients show signs or symptoms of immune-response-related adverse events including anaphylaxis (Section 6.4.3) and mucocutaneous reaction (Section 6.4.5)

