### 18.1. ADA

The incidence of ADA and neutralizing antibody at Day 1 pre-dose and at Weeks 2 pre-dose, 3 pre-dose, 4 pre-dose, Week 5, 12, 20, 28, 36, and 52 (EOS) will be summarized by treatment group and visit.

- Incidence (%)= number of subjects with specific assessment result/ number of subject with available assessment results \* 100%

ADA and neutralizing antibody results by visit as well as the overall positive of ADA and neutralizing antibody from Day 1 will be summarized. Patients with at least one positive result up to Week 28 (or Week 52) from (and including) Day 1 will be considered as overall positive; Otherwise, patients without any positive result up to Week 24 (or Week 52) from (and including) Day 1 will be considered as overall negative.

For each treatment group, the proportion of response, 95% CI for the proportion, proportion difference between SAIT101 and MabThera®, standard deviation, and 95% CI for the proportion difference will be reported. The Wilson Score method will be used to calculate 95% CI.

- Response:
  - ADA positive
  - ADA negative
  - Neutralizing antibody positive
  - Neutralizing antibody negative

Listings for ADA assessments by patient will be provided.

---

Document:

Author:

Version Number:

Version Date:

Final v1.0

10Sep2019

Template No: CS\_TP\_BS016 Revision 4

Effective Date: 01Apr2016

Reference: CS\_WI\_BS005

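### Appendix 10 restricts antibody sampling during treatment to Day 15, while Table 1, the synopsis and the SAP require Days 8, 15 and 22

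*Protocol*

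**What the plan says.** Protocol Appendix 10 is a visit-by-visit checklist with the same title as Table 1. Its section 2.2 is headed "Treatment Visits (Visits 3, 4, and 5 – Study Days 8, 15 and 22") and contains the line "Immunogenicity sampling prior to dosing (Day 15 only"). The IgG/IgM line just above it carries no day limit. For Day 1, section 2.1 asks for a pre-dose sample without restriction.

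Four other places give a different schedule:

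- **Protocol synopsis:** "Immunogenicity sampling is to be done at Weeks 1, 2, 3, 4, 5, 12, 20, 28, 36, and 52 (EOS").
- **Protocol Table 1:** the immunogenicity row is marked at all ten of those weeks, and the header equates Weeks 2, 3 and 4 with Days 8, 15 and 22. Footnote w says: "On infusion visits, the sample should be collected pre-dose".
- **Protocol section 5.3:** samples of about 5 to 8 mL are taken at the Table 1 visits, for a total of about 80 mL per patient.
- **SAP 18.1:** antibody and neutralizing antibody incidence is summarized "at Day 1 pre-dose and at Weeks 2 pre-dose, 3 pre-dose, 4 pre-dose, Week 5, 12, 20, 28, 36, and 52 (EOS").

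**The concern.** A parenthesis that names one of three visits reads as a deliberate exclusion of the other two. Whether a patient has Day 8 and Day 22 samples would then depend on which page the site uses.

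Immunogenicity is a secondary objective of this biosimilar comparison, and the SAP handles a missing sample in two different ways:

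- **By visit (SAP 18.1):** the denominator is patients with an available result. Week 2 and Week 4 incidence would then come only from sites that followed Table 1.
- **Overall status (SAP 15 and 18.1):** a patient with no positive result is classed as negative, with no minimum number of samples. An uncollected sample silently counts towards negative, so a patient sampled eight times has fewer chances to be found positive than one sampled ten times.

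Overall status is used in the between-arm difference and its 95% CI (SAP 18.1), the PK summaries and covariate sensitivity analysis (SAP 13.2), the exploratory analysis of antibodies on PK and PD (SAP 15) and the response-rate subgroup analysis (SAP 16.3).

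**Working it through.** **1. Schedules side by side**

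| Source | Weeks sampled | Count |
|---|---|---|
| Synopsis, Table 1, SAP 18.1 | 1, 2, 3, 4, 5, 12, 20, 28, 36, 52 | 10 |
| Appendix 10 (sections 2.1 to 2.4) | 1, 3, 5, 12, 20, 28, 36, 52 | 8 |

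The difference is Week 2 (Day 8) and Week 4 (Day 22). The early-discontinuation and unscheduled visits in Table 1 are not counted here.

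**2. Which schedule reproduces the stated blood volume**

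Inputs from Protocol section 5.3: 5 to 8 mL per sample, about 80 mL in total. Formula: number of samples × volume per sample.

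- Ten samples: 10 × 5 = 50 mL to 10 × 8 = 80 mL. The stated total is reached at the upper end.
- Eight samples: 8 × 5 = 40 mL to 8 × 8 = 64 mL. The stated total is not reached; it would need 80 / 8 = 10 mL per sample, outside the stated range.

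**3. Whether the protocol counts volumes this way elsewhere**

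PK and PD samples are about 5 mL each, taken twice at each of the four infusion visits and once at later visits.

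- PK (Weeks 5, 12, 20 and 28 after the infusions): (4 × 2 + 4) × 5 = 60 mL. Section 5.4 states about 60 mL.
- PD (the same plus Weeks 36 and 52): (4 × 2 + 6) × 5 = 70 mL. Section 5.5 states about 70 mL.

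Both totals are reproduced by counting scheduled Table 1 visits only.

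**4. Samples at risk**

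- Per patient: 2 / 10 = 20%.
- Over 308 randomized patients: 2 × 308 = 616 of 10 × 308 = 3,080.

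The 616 is a ceiling. It assumes that every site follows the appendix and that every patient attends all ten visits. The documents do not say what share of sites would do so, so the range is 0 to 616.

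**The case against.** The strongest reply is that the protocol already points sites to Table 1. Section 3.1 refers to Table 1 for the assessments at each visit, section 5.3 does so for immunogenicity samples specifically, and SAP 2.5 names it as the schedule of events. On that reading the appendix line is a stray error that few sites would act on. This stands as an argument about likelihood, and it supports the direction of the correction. It does not remove the contrary instruction: no clause gives Table 1 precedence, and the appendix is an operational checklist under the same title.

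The blood volume is approximate. Eight scheduled draws plus one at early discontinuation and one unscheduled would also give 10 × 8 = 80 mL. The PK and PD totals count scheduled visits only, which makes that reading less likely, but the volume remains supporting evidence rather than proof. The contradiction does not depend on it.

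The consequences are also bounded. By visit, a missed sample lowers the denominator and is not counted as negative. Eight time points are sampled under either text, so overall status changes only for a patient positive solely at Week 2 or Week 4, and the documents give no figure for how often that happens. Allocation is blinded and 1:1, so the loss should fall on both arms alike in expectation, and the antibody comparison has no equivalence criterion. All of this is correct and limits the severity. Equal under-detection is not neutral, however: if the same fraction of positives is missed in each arm, any true difference in overall incidence shrinks by that fraction, towards apparent similarity.

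**Conclusion.** The concern holds. Appendix 10 section 2.2 is incompatible with Table 1 and its footnote w, with the synopsis, and with the time points the SAP tabulates; nothing in either document reconciles them. This is an internal inconsistency, not a matter of design preference.

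Its certain size is two scheduled samples per patient, 20% of the planned ten. The number actually lost depends on site behaviour that the documents do not describe. The effect is confined to the Week 2 and Week 4 antibody and neutralizing antibody summaries and, less directly, to overall antibody status and the analyses that use it. Power and sample size for the Week 28 response rate are unaffected. The point should be corrected, but it does not threaten the primary conclusion.

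**What to change.** Reconcile Appendix 10 section 2.2 with Table 1, the synopsis and SAP 18.1. If those three stand, delete the parenthetical restriction to Day 15, so that the line covers all three treatment visits as the Day 1 line covers Day 1.

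If samples have already been collected under the present text, report the number of patients with a result at each visit by arm and the number of samples per patient. Add a sensitivity summary of overall antibody status using only the eight visits common to both schedules.

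The text change is one phrase. Table 1 already schedules the samples and section 5.3's blood volume accommodates them, so nothing is added for patients beyond Table 1. Protocol section 10.7 requires a permanent change to go through an amendment; the sponsor would judge whether this one counts as administrative, and it could travel with the next amendment alongside a prompt clarification to sites.
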